8.1 Efficacy and Safety assessments

8.1.1 Efficacy Assessment

Objective Response

All patients who receive Acalabrutinib capsule 100 mg BID will be evaluated for efficacy once every 03 months during the treatment phase. The following assessments must be performed every three treatment cycles: tumour assessment, ECOG performance status, and partial remission (PR), partial response with lymphocytosis (PR-L) and complete remission (CR).

A characteristic feature of BTK inhibitor is that it may transiently increase the peripheral lymphocyte count while the lymph nodes are shrinking and patients are improving. Some patients were taken off study very early in ibrutinib trials because their lymphocyte count began to go up and it was assumed that they were progressing. The transient lymphocytosis is now understood to be an effect of redistributing parts of the disease into the blood. It is not considered as a sign of disease progression. There is now a response criterion known as PRL, which refers to patients who have a greater than 50% shrinkage of nodal disease and who fulfil all criteria of partial response (PR) except for a persistent lymphocytosis. (Woyach et al., 2014) In the present study the objective response will evaluate PR, PR-L, and CR.

The efficacy endpoint will be objective response, defined as the proportion of patients achieving either a PR or CR per the iwCLL 2018 criteria for CLL/SLL (Hallek et al., 2018) and Lugano classification for NHL for MCL (Cheson et al., 2014) as presented in Table 4 and Table 5, respectively. Efficacy will be based on objective response [Complete Remission (CR) + Partial Remission (PR)] via Computed Tomography (CT) scans or Magnetic Resonance Imaging (MRI).

Table 4: Response (CR and PR) definition after treatment of CLL/SLL patients (Hallek et al., 2018)

Parameter	Complete Remission (CR)	Partial Remission (PR)
Lymph nodes	None ≥ 1.5 cm	Decrease $\geq 50\%$ from baseline*
Liver and/or spleen size†	Spleen size < 13 cm; liver size normal	Decrease $\geq 50\%$ from baseline
Constitutional symptoms	None	any
Circulating lymphocyte count	Normal	Decrease $\geq 50\%$ from baseline
Platelet count	$\geq 100 \times 10^9/L$	$\geq 100 \times 10^9/L$ or increase $\geq 50\%$ over baseline
Haemoglobin	≥ 11.0 g/dL (untransfused and without erythropoietin)	≥ 11.0 g/dL or increase $\geq 50\%$ over baseline

*Sum of the products of 6 or fewer lymph nodes (as evaluated by CT scans and physical examination in clinical trials or by physical examination in general practice).

†Spleen size is considered normal if, it is < 13 cm. There is no firmly established international consensus of the size of a normal liver; therefore, liver size should be evaluated by imaging and manual palpation

A CT-based Response Assessment Criteria for MCL will be assessed as per Table 5 (Cheson et al., 2014). Patients with abnormalities of blood parameters without any lymphadenopathy or organomegaly will not undergo CT or MRI scans. Patients who will be undergoing CT, should have baseline and every 3-months reports.

Table 5: Response Assessment Criteria for MCL patients

Response and Site	Complete Response	Partial Response
Lymph nodes and extra lymphatic sites	Target nodes/nodal masses must regress to ≤ 1.5 cm in LDi No extra lymphatic sites of disease	$\geq 50\%$ decrease in SPD of up to 6 target measurable nodes and extra-nodal sites When a lesion is too small to measure on CT, assign 5 mm \times 5 mm as the default value When no longer visible, 0 \times 0mm For a node > 5 mm \times 5 mm, but smaller than the normal, use the actual measurement for calculation
Non-measured lesion	Absent	Absent/normal, regressed, but no increase

Response and Site	Complete Response	Partial Response
Organ enlargement	Regress to normal	Spleen must have regressed by > 50% in length beyond normal
New lesions	None	None

LDI: longest transverse diameter of a lesion; SPD: sum of the product of the greatest diameters

Patient-Reported Outcome

A health-related quality of life questionnaire i.e., QLQ-C30 Questionnaire will be administered to each subject at screening/visit 1 before the dosing, every three months during the treatment period and at the end of the study. Most of the items in the questionnaire use a “past week” recall period. The patients will be assessed on the functional, symptoms, and global quality of life scale.

8.1.2 Safety assessments

Safety evaluations will include clinical laboratory parameters (haematology and biochemistry), physical examinations, vital sign measurements, ECG monitoring, ECOG performance status, adverse event monitoring, and death, as observed by the Investigator. Based on the previous *in vitro* studies, animal toxicological findings, and human studies with Acalabrutinib, arrhythmias (which includes atrial fibrillation), anaemia, hypertension, bleeding, infections, and second primary malignancies will be closely monitored. Any of the safety monitoring assessments may be performed more frequently, and adverse events should be evaluated by the Investigator according to the standard practice if clinically indicated.

Clinical safety laboratory assessments

The list of clinical safety laboratory tests to be performed are provided in Table 6 and Table 7. All protocol-required laboratory assessments, as defined in the table, must be conducted in accordance with the laboratory manual and the timing and frequency outlined in the SoA.

The Investigator should assess the available results with regard to clinically relevant abnormalities. The laboratory results should be signed, dated, and retained at the site as source data for laboratory variables.

For information on how AEs based on laboratory tests should be recorded and reported, refer Section 8.2.7.

Additional safety samples may be collected if clinically indicated at the discretion of the Investigator. The date, time of collection, and results (values, units, and reference ranges) should be appropriately recorded in the eCRF.

The haematology (Table 6), clinical chemistry (Table 7) and urinalysis (routine and microscopy) measurements will be performed at a local laboratory at or near the Investigator site.

A complete blood cell count will be conducted as per SoA (Table 1). It includes white blood cell count, haemoglobin, haematocrit, reticulocyte, platelet count and differential leukocyte count, including both percent and an absolute number of lymphocytes.

Table 6: Haematology

Haematocrit
Haemoglobin
Basophils
Eosinophils
Monocytes
Lymphocytes
Reticulocytes
Absolute Neutrophil Count
Platelet count
Total leucocyte count

Table 7: Clinical chemistry (serum or plasma)

Albumin
Glucose
Amylase
Lipase
Alkaline phosphatase
Lactate dehydrogenase
Alanine aminotransferase
Aspartate aminotransferase
Potassium
Bicarbonate
Sodium
Calcium
Total bilirubin
Chloride
Total protein
Creatinine (creatinine clearance)
Urea or Blood Urea Nitrogen, depending on local practice
Gamma-glutamyl transferase
Magnesium
Haptoglobin
b2-microglobulin

Note: CMV serology, HIV (anti-HIV1 Ab, anti-HIV2 Ab), Hepatitis serology testing will be conducted at the screening that includes hepatitis B surface antigen (HBsAg), hepatitis B surface antibody (HBsAb), anti-HBc, and HCV antibody.

The local GLP certified laboratory will perform haematology and clinical chemistry tests. Additional analyses may be performed if clinically indicated.

Any clinically significant abnormal laboratory values should be repeated as clinically indicated and recorded in the eCRF.

All patients who have any Common Toxicity Criteria (CTC) Grade 3 or 4 laboratory values at the time of completion or discontinuation from study must have further tests performed until the laboratory values have returned to CTC Grade 1 or 2, unless these values are not likely to improve because of the underlying disease.

Urine Pregnancy Test

Urine pregnancy tests will be required only for women of childbearing potential. Urine pregnancy tests will be performed at Screening; on Cycle 1 Day 1; on Day 28 of Cycles 1-6; and at the early termination or End of study visit.

Physical examinations

For timing of individual measurements refer to the schedule outlined in (Table 1).

A complete physical examination will be performed and will include an assessment of the following (as clinically indicated): general appearance, respiratory, cardiovascular, abdomen, skin, head, neck (including ears, eyes, nose, and throat), lymph nodes, thyroid, musculoskeletal (including spine and extremities), and genital/rectal and neurological systems.

Symptom-directed physical exams, including tumour assessments by palpation, will be done during the treatment period and at the EOT visit.

Lymph nodes: The bi-dimensional diameters of the largest palpable lymph node/s in each of the following sites should be recorded: cervical, axillary, and inguinal. The dimensions of the liver and spleen below their respective costal margins, as assessed by palpation, should also be recorded.

Performance status will be assessed using ECOG performance status.

Vital signs

The timings of assessments for vital signs are provided in Table 1 (SoA). Patients will be monitored with the assessment of vital signs (Blood Pressure, pulse, respiratory rate, and temperature) at screening and at each subsequent visit in the treatment phase. Additional monitoring with the assessment of vital signs is at the discretion of the Investigator per standard clinical practice or as clinically indicated. The date and time of collection and measurement will be recorded in the eCRF.

Electrocardiograms (ECG)

Resting 12-lead ECGs will be recorded at screening and as clinically indicated throughout the study. ECGs should be obtained after the patient has been rested in a supine position for at least 5 minutes and recorded while the patient remains in that position. In case of clinically significant ECG abnormalities, including a QTc value >480 ms, 2 additional 12-lead ECGs should be obtained over a brief period (e.g., 30 minutes) to confirm the finding.

All ECGs should be assessed by the Investigator for clinically significant abnormalities. If there is a clinically significant abnormal finding, the Investigator will record it as an AE on the eCRF.

At screening, the mean QTc with Bazett's correction ($QTcB = QT/\sqrt{R}$) must be <480 msec as per the eligibility criteria of the study.

Chest X-Ray

Patients with signs and symptoms of Pneumonia will be allowed to go for chest X-ray investigation. A symptom directed chest X-ray will be conducted at screening and all subsequent visits during the study duration.

8.2 Collection of adverse events

The Principal Investigator is responsible for ensuring that all staff involved in the study are familiar with the content of this section. The definitions of an AE or SAE can be found in Appendix B.

All adverse events occurring during the study will be recorded and reported. AEs observed/elicited by the Physician/ Site Investigator during physical examination and vital signs recording or derived from safety assessments; reported by patients during site visits will be documented in the source notes and in the AE log of eCRF. AEs can be reported by the patient (or, when appropriate, by a caregiver, surrogate, or the patient's legally authorized representative).

The Investigator and any designees are responsible for detecting, documenting, and recording events that meet the definition of an AE or SAE. For information on how to follow-up AEs, refer Section 8.2.3.

The nature of adverse events will be recorded in the eCRF. This will include reporting of duration, severity, seriousness, causality/ relationship with the study drug, action taken in terms of any medication or any other intervention and outcome of the event. These assessments will be performed by the Physician/Site Investigator. In the event an AE is being assessed in real time and a Co-Investigator (other than the Site Investigator) is evaluating the event, then the final conclusion on the nature of AE can be revised based on the judgement arrived at by the Site Investigator.

The events will be coded by the data management team using Medical Dictionary for Regulatory Activities (MedDRA) version 20.0 or above.

8.2.1 Method of detecting AEs and SAEs

Care will be taken not to introduce bias when detecting AEs and/or SAEs. Open-ended and non-leading verbal questioning of the patient is the preferred method to inquire about AE occurrences.

8.2.2 Time period and frequency for collecting AE and SAE information

Adverse events and SAEs will be collected from the time of signature of informed consent, throughout the treatment period (168 days), End of study visit (Day 170) and including the follow-up period (28 days after the last dose of study drug) in patients who discontinue before 168 days.

If a patient discontinues from study drug for reasons other than disease progression, drug-related SAEs must be captured until the patient is initiated on an alternate intervention or up to 28 days, whichever is earlier.

All SAEs will be recorded and reported to the Sponsor or designee within 24 hours, as indicated in Appendix B. The Investigator will submit any updated SAE data to the Sponsor within 24 hours of it being available.

Investigators are not obligated to actively seek AE or SAE in former study patients. However, if the Investigator learns of any SAE, including death, at any time after a patient's last visit and he/she considers the event to be reasonably related to the study treatment or study participation, the Investigator may notify the Sponsor.

The method of recording, evaluating, and assessing causality of AE and SAE and the procedures for completing and transmitting SAE reports are provided in Appendix B.

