1. PROTOCOL SUMMARY

1.1 Schedule of Activities (SoA)

Table 1: Schedule of Activities (SoA)

Study Phase	Screening Phase	Treatment Phase ^a		Follow-up Phase
Cycle		Cycles 1-6	EOT	EOS
Visit No.	1	2-7 (Day 1 of each cycle)	8	
Study Days	-6 to 0	1-168 (28 days per cycle)	170	28 days post-EOT
Screening/Enrolment visit				
Informed consent ^s	X			
Eligibility Criteria	X			
Demographics/ Review medical history	X			
ECOG Performance Status	X	X	X	
General Physical examination ^b	X	Symptom-directed physical examination only		
Concomitant medication recording	Continuous from the time of ICF until 28 days after the last Acalabrutinib dose in the treatment phase.			
Study Drug Administration				
Acalabrutinib dosing		The recommended dose is Acalabrutinib 100 mg capsules BID, starting on Day 1 Cycle 1, until disease progression or unacceptable toxicity. Each cycle of treatment is 28 days.		
Disease Evaluations (Disease characteristics will be performed as per routine clinical practice)				
Baseline Disease Characteristics	X			
Safety Evaluations (baseline and each treatment visit) [*]				
Physical examination ^b	X	Symptom-directed physical examination only		
Vital parameters ^c	X	X	X	
Adverse event monitoring	Continuous from the time of ICF until 28 days after last study dose of Acalabrutinib.			

Study Phase	Screening Phase	Treatment Phase ^a		Follow-up Phase
Cycle		Cycles 1-6	EOT	EOS
Visit No.	1	2-7 (Day 1 of each cycle)	8	
Study Days	-6 to 0	1-168 (28 days per cycle)	170	28 days post-EOT
12-lead ECG	X	X	X	
Lymph node biopsy ^d	X			
Next-generation sequencing (NGS)-CLL panel ^e	X			
Haematology ^f & Biochemistry ^g	X	X	X	
Urinalysis ^h	X	X	X	
Pregnancy Test ⁱ	X	X	X	
Chest X-ray ^j	X	X	X	
Efficacy Evaluations (once in 3 months)				
CT/MRI ^k	X	X	X	
EORTC QLQ-C30 Questionnaire	X	X	X	

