Patients who are observed to receive clinical benefit from Acalabrutinib after completion of treatment phase, may continue to receive Acalabrutinib, if in the opinion of their treating physician they are continuing to derive clinical benefit from continued treatment or have not progressed clinically. The patients may continue treatment via drug supply (provided by AstraZeneca) until disease progression or withdraw of drug due to side effects or investigators decision whichever comes first.

These subjects shall receive the study drug free of cost in case if there is no coverage / reimbursement through a separate patient support program and will not receive the medication via the clinical trial supply for this study. These subjects shall not be actively monitored for AE's and it will be the responsibility of the treating physician to ensure reporting of all SAE's,

pregnancies, overdose and medication errors to the relevant authorities as per the standard spontaneous safety reporting practice in India.

Safety Evaluations

Safety evaluations will include adverse event monitoring, physical examinations, ECG monitoring, clinical laboratory investigations (haematology and biochemistry), vital sign measurements, ECOG performance status, and death as observed by the Investigator. Based on previous *in vitro* studies, animal toxicological findings, and human studies with Acalabrutinib, arrhythmias (which includes atrial fibrillation), anaemia, hypertension, bleeding, infections, and second primary malignancies will be closely monitored. Any of the safety monitoring assessments may be performed more frequently, and adverse events should be evaluated by the Investigator according to the standard practice if clinically indicated.

Efficacy Evaluations

All patients who receive Acalabrutinib capsule 100 mg BID will be evaluated for efficacy once every 03 months during the treatment phase. Efficacy will be assessed based on iwCLL 2018 criteria for CLL/SLL (Hallek et al., 2018) and for MCL (Cheson et al., 2014). Efficacy will be based on objective response [Complete Remission (CR) + Partial Remission (PR) and partial response with lymphocytosis (PRL)] via Computed Tomography (CT) scans or Magnetic Resonance Imaging (MRI).

Statistical methods:

Sample Size Justification

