4.1.3 End-of-Treatment Visit (EOT)

An End-of-Treatment Visit will be scheduled on Day 170 (Visit 8) of the study. All patients who will complete the Treatment phase will be assessed for EOT. In the event where a patient discontinues the study treatment for any reason listed in Section 7.1 before Day 168, the last visit of the patient will be considered as the End-of-Treatment Visit and the patient will be assessed as per EOT visit.

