4.1.4 Follow-Up Phase (End-Of-Study)

The Follow-up Phase will begin once a patient discontinues study drug or completes the Treatment Phase. The follow-up phase will continue until 28 days after last dose, loss to follow up, withdrawal of consent for study participation, or end of the study, whichever occurs earlier. A follow-up will be conducted 28 days after the EOT visit via a phone call. This will be considered as End-of-Study Visit. Every effort should be made to conduct the End-of-Study Visit.

Patients who are observed to receive clinical benefit from Acalabrutinib after completion of treatment phase, may continue to receive Acalabrutinib, if in the opinion of their treating physician they are continuing to derive clinical benefit from continued treatment or have not progressed clinically. The details on “Post-Trial Access” are provided in section 1.2.

For details on treatments given during the study, refer Section 6.1 Treatments Administered.

For details on what is included in the efficacy and safety endpoints, refer Section 3 and 8.

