4.4 End of study definition

The end of the study is defined as the last expected visit/contact of the last patient undergoing the study.

A patient is considered to have completed the study when he/she has completed his/her last scheduled visit or last scheduled procedure shown in the SoA

Refer Appendix A 6 for guidelines for the dissemination of study results.

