Immediate safety concerns should be immediately discussed with the Sponsor upon occurrence or awareness to determine if the patient should continue or discontinue study treatment.

Adherence to the study design requirements, including those specified in the SoA, is essential and required for study conduct.

All screening evaluations must be completed and reviewed to confirm that potential patients meet all eligibility criteria. The Investigator will maintain a screening log to record details of all patients screened, confirm their eligibility for the trial, or record reasons for screening failure, as applicable.

Procedures conducted as part of the patient's routine clinical management (e.g., blood count) and obtained before signing of the ICF may be utilised for screening or baseline purposes provided the procedures meet the protocol-specified criteria and were performed within the time frame defined in the SoA.

The maximum amount of blood collected from each patient will not exceed approximately 10 mL/visit. Repeat or unscheduled samples may be taken for safety reasons or for technical issues with the samples

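### Section 8.2.2 ends completers' adverse event collection at Day 170, while the Schedule of Activities runs it to 28 days after the last dose for every patient

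*Protocol*

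**What the plan says.** Four places in the documents set the adverse event (AE) window or the visits that bound it.

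- **Protocol 8.2.2**, the section on the timing of AE collection, runs from consent through the 168 treatment days to an "End of study visit (Day 170"). It then adds one further period, with a limit on who gets it: "and including the follow-up period (28 days after the last dose of study drug) in patients who discontinue before 168 days".
- **Protocol Table 1 (section 1.1)** gives the AE monitoring window as "Continuous from the time of ICF until 28 days after last study dose of Acalabrutinib". SAP section 2.2.5 repeats that row. Neither separates completers from early stoppers.
- **Protocol 4.1.3** says "An End-of-Treatment Visit will be scheduled on Day 170 (Visit 8) of the study".
- **Protocol 4.1.4** puts both discontinuers and completers into the Follow-up Phase and says "A follow-up will be conducted 28 days after the EOT visit via a phone call". It names that call the End-of-Study Visit.

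The primary endpoint, in the Synopsis and in section 9.2, is the incidence of serious and non-serious AEs observed during the trial. SAP section 6.3.1 summarises AEs by frequency and percentage and sets no time window for counting them.

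**The concern.** Section 8.2.2 gives the 28-day post-dose period only to patients who stop early. The natural reading is that a completer's collection ends at Day 170, two days after the last dose. Table 1 says otherwise, and a site could cite either text.

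The wrong visit label makes this worse. Section 8.2.2 also says investigators need not actively look for AEs in former study patients. A site that takes Day 170 as the end of study could treat completers as former patients from that day, although the end-of-study call is still four weeks away.

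At stake is the collection window for non-serious AEs in a trial whose main purpose is to estimate AE incidence. The window could differ from site to site, and the SAP has no counting rule that would make it uniform at analysis. An analysis rule could not recover events that were never collected in any case.

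**Working it through.** **1. Reproduce the plan's own figure.** Six cycles × 28 days = 168 days, which matches the treatment period in section 8.2.2.

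**2. Date the end of a completer's window under each text** (last dose on Day 168).

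| Source | Rule | End of window |
|---|---|---|
| Protocol 8.2.2 | Day 170 visit; the extra 28 days only for those stopping before Day 168 | Day 170 |
| Protocol Table 1, SAP 2.2.5 | Last study dose + 28 days, all patients | 168 + 28 = Day 196 |
| Protocol 4.1.4 | End-of-study call at end-of-treatment visit + 28 days | 170 + 28 = Day 198 |

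**3. Size of the gap.** 196 − 170 = 26 days, and 26/196 = 13.3% of the Table 1 window counted from Day 1. The call on Day 198 falls two days after that window closes, so one call can cover all of it.

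**4. Effect on incidence.** The documents give no AE rates for this trial, so the rates here are assumptions. Let *p* be the proportion with a first event by Day 168 and assume a constant hazard to Day 196. First events missed per 100 patients, if collection stops at Day 170:

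100 × [(1 − p)^(170/168) − (1 − p)^(196/168)]

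| Assumed p | All patients affected, nothing recovered | Half recovered at the call | One of 10 equal-sized sites affected |
|---|---|---|---|
| 5% | 0.75 | 0.38 | 0.08 |
| 20% | 2.71 | 1.35 | 0.27 |
| 50% | 5.04 | 2.52 | 0.50 |

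The first column is an upper bound under this model, because it treats every patient as a completer at a site that stops at Day 170. At p = 20%, cumulative incidence is 20.21% by Day 170 and 22.92% by Day 196. Setting the rate at Day 196 instead gives a similar answer: a true 20% would be seen as 17.6%, or 2.4 per 100.

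**5. Compare with sampling error.** The exact 95% interval for 20 events in 100 patients is 12.67% to 29.18%. This agrees with protocol Table 8. The worst-case shift at p = 20% is well inside it.

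**The case against.** The strongest reply is that section 8.2.2 is the outlier and the rest of the protocol covers the gap.

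- Section 8 says "Adherence to the study design requirements, including those specified in the SoA, is essential and required for study conduct", and the schedule carries the 28-day window.
- Section 8.2 requires all AEs during the study to be recorded, and section 8.2.3 asks for proactive follow-up of AEs in each patient.
- Section 4.1.2 calls the post-treatment period a safety follow-up phase, and section 4.1.4 puts completers in it.
- Section 8.2.2 could be naming the right visit with the wrong day, since section 4.1.4 defines the End-of-Study Visit as the call.

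Most of this stands, and it makes actual loss of data less likely. It does not remove the contradiction. The day number is explicit, and so is the limit to patients who stop early. The general rule in section 8.2 gives no end day, and section 4.1.4 does not say what is asked at the call.

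A reader might also draw four stronger conclusions. The documents do not support them.

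- *Collection could stop at Day 168.* Section 8.2.2 includes Day 170, and section 4.1.3 requires the end-of-treatment assessment for all completers.
- *The post-trial access text ends active collection when treatment ends.* The Synopsis says of patients continuing on drug, "These subjects shall not be actively monitored for" AEs. But that text concerns access after the trial, and under section 4.4 a patient completes the study once he or she "has completed his/her last scheduled visit or last scheduled procedure shown in the SoA". It can fairly be read as starting after study exit.
- *Serious events and deaths would be lost.* Sections 8.3.1 and 8.2.7 have their own reporting rules for these.
- *A comparison of completers with early stoppers would be biased.* None is planned. The columns of SAP Table 14.3.1 are CLL/SLL, MCL and Total. Early stoppers are not uniformly followed for 28 days either, because section 7.1 ends their follow-up sooner if a new anti-cancer treatment starts.

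**Conclusion.** The contradiction is real and stands in the current text. Section 8.2.2 restricts the 28-day collection to early discontinuers and gives Day 170 the wrong name, against Table 1, SAP 2.2.5 and sections 4.1.3 and 4.1.4. A site following it literally could leave up to 26 of 196 days (13.3%) uncollected for a completer's non-serious AEs.

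The likely effect on reported incidence is small. The upper bounds of 0.75, 2.7 and 5.0 missed first events per 100 rest on assumed incidences of 5%, 20% and 50%, a constant hazard, universal completion and no recovery at the call. The constant hazard is untested for patients who stop the drug at Day 168. The documents do not show how many sites would follow 8.2.2 over Table 1. The 168-day treatment phase stays fully observed, and no hypothesis is tested. The text should be corrected because it misstates the collection window of the primary endpoint. It does not put the trial's conclusions in doubt.

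**What to change.** In protocol section 8.2.2:

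1. Delete the words that restrict the 28-day period to patients who stop before 168 days.
2. State that AE and SAE collection runs, for all patients, to 28 days after the last dose of the treatment phase and is completed at the end-of-study call.
3. Relabel Day 170 as the end-of-treatment visit.

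Tying the window to the last treatment-phase dose also settles it for patients who continue on post-trial supply. A sentence in the post-trial access text, saying that spontaneous-only reporting starts after the call, would be an optional clarification.

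The cost is a minor amendment with the ethics approval that Appendix A 1 requires, and a few more AE records. The call is already scheduled. Sample size and Table 8 do not change. One limit remains: Table 1 schedules no laboratory tests, vital signs or ECG at end of study, so the call will pick up events that patients notice and report, not silent ones.

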9.2 Sample size determination

The primary endpoint of the trial is to demonstrate the safety profile of Acalabrutinib in routine clinical practice as assessed by the incidence of adverse events (AEs) (Serious and Non-serious) observed during the trial. As per the Health Authority requirement, the total sample size of the study is approximately 100.

The table below illustrates the estimated incidence and the precision of the estimate that could be expected for a variety of sample sizes (indicative of possible subgroup and total sample) for an observed number of patients with a particular event.

Table 8: Estimated Incidence and Precision

Number of observed events	Estimated incidence/precision*				
	n=10	n=20	n=50	n=90	n=100
0	0.0% (0.00%, 30.85%)	0.0% (0.00%, 16.84%)	0.0% (0.00%, 7.11%)	0.0% (0.00%, 4.02%)	0.0% (0.00%, 3.62%)
1	10.0% (0.25%, 44.50%)	5.0% (0.13%, 24.87%)	2.0% (0.05%, 10.65%)	1.1% (0.03%, 6.04%)	1.0% (0.03%, 5.45%)
2	20.0% (2.52%, 55.61%)	10.0% (1.23%, 31.70%)	4.0% (0.49%, 13.71%)	2.2% (0.27%, 7.80%)	2.0% (0.24%, 7.04%)
3	30.0% (6.67%, 65.25%)	15.0% (3.21%, 37.89%)	6.0% (1.25%, 16.55%)	3.3% (0.69%, 9.43%)	3.0% (0.62%, 8.52%)
4	40.0% (12.16%, 73.76%)	20.0% (5.73%, 43.66%)	8.0% (2.22%, 19.23%)	4.4% (1.22%, 10.99%)	4.0% (1.10%, 9.93%)
10	100.0% (69.15%, 100%)	50.0% (27.20%, 72.80%)	20.0% (10.03%, 33.72%)	11.1% (5.46%, 19.49%)	10.0% (4.90%, 17.62%)
20		100.0% (83.16%, 100%)	40.0% (26.41%, 54.82%)	22.2% (14.13%, 32.21%)	20.0% (12.67%, 29.18%)
30			60.0% (45.18%, 73.59%)	33.3% (23.74%, 44.05%)	30.0% (21.24%, 39.98%)
40			80.0% (66.28%, 89.97%)	44.4% (33.96%, 55.30%)	40.0% (30.33%, 50.28%)
50			100.0% (92.89%, 100%)	55.6% (44.70%, 66.04%)	50.0% (39.83%, 60.17%)

* Clopper-Pearson exact 95% confidence interval

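### Protocol 8.2.2 ends adverse event collection for completers at Day 170, in conflict with the 28-day follow-up in Table 1, the SAP study plan and Section 4.1.4, and leaves the scope for early discontinuers ambiguous.

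*Protocol*

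**What the plan says.** Protocol 9.2 defines the primary endpoint as the safety profile "as assessed by the incidence of adverse events (AEs) (Serious and Non-serious) observed during the trial". These places bear on how long AEs are collected:

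- **Protocol Table 1 (1.1), repeated in SAP 2.2.5.** AE monitoring is "Continuous from the time of ICF until 28 days after last study dose of Acalabrutinib". Completers and early discontinuers are not distinguished.
- **Protocol 8.2.2, first paragraph.** AEs and SAEs are collected from consent "throughout the treatment period (168 days), End of study visit (Day 170", and then "including the follow-up period (28 days after the last dose of study drug) in patients who discontinue before 168 days".
- **Protocol 8.2.2, second paragraph.** After discontinuation for a reason other than progression, "drug-related SAEs must be captured until the patient is initiated on an alternate intervention or up to 28 days, whichever is earlier".
- **Protocol 4.1.3 and 4.1.4.** Day 170 is the EOT visit. "The Follow-up Phase will begin once a patient discontinues study drug or completes the Treatment Phase". "A follow-up will be conducted 28 days after the EOT visit via a phone call", and that call is the End-of-Study visit.
- **Protocol 7.1.** For patients discontinued from the study, follow-up ends at the earlier of a new anticancer intervention or 28 days.
- **Protocol 1.2, post-trial access.** Of patients who continue the drug after the treatment phase: "These subjects shall not be actively monitored for AE's".
- **SAP 6.3.1.** AEs, SAEs and AEs of special interest are tabulated as counts and percentages. No analysis window is given.

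**The concern.** An incidence has no fixed meaning until the time at risk is fixed. Here the answer for completers depends on the page consulted: Day 170 in 8.2.2, or 28 days after the last dose in Table 1. Section 8.2.2 is the section devoted to the AE collection period, so a site could reasonably apply it as written. Ten sites are planned. If they choose differently, the pooled percentage mixes two windows, and nothing in the SAP would detect or correct that.

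The interim analysis in SAP 2.5 makes this more pressing: it reports the primary safety analyses for the first 50 patients who complete the study, the group whose window is in dispute.

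The second paragraph of 8.2.2 adds a separate uncertainty about which events are collected after early discontinuation for reasons other than progression.

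**Working it through.** **1. The plan's own figures.** The documents give no calculation for the window. The only computed figures behind the primary endpoint are the exact intervals in Protocol Table 8. With x events in n patients, the Clopper-Pearson lower limit is the 0.025 quantile of Beta(x, n−x+1), and the upper limit is the 0.975 quantile of Beta(x+1, n−x). All 43 cells reproduce to two decimals; for example, 10 of 100 gives 4.90% to 17.62%. The sample size of about 100 is set by the Health Authority. Neither it nor Table 8 depends on the window.

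**2. Window ends for a completer.** Six cycles of 28 days put the last treatment-phase dose on Day 168.

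| Source | Arithmetic | Last day |
|---|---|---|
| 8.2.2, first paragraph, literal | as stated | 170 |
| Table 1 and SAP 2.2.5 | 168 + 28 | 196 |
| End-of-Study call, 4.1.4 | 170 + 28 | 198 |

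Section 8.2.2 covers 170 − 168 = 2 post-dose days. Against Table 1 the gap is 196 − 170 = 26 days, which is 26/28 = 92.9% of the post-dose follow-up and 26/196 = 13.3% of Days 1 to 196. The call on Day 198 falls after Day 196, so it can collect the whole Table 1 window.

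**3. Illustrative effect on incidence.** Two assumptions are needed that the documents do not supply: a constant hazard over Days 1 to 196, and a range of true Day 196 incidences p. The incidence recorded if collection stops at Day 170 is then q = 1 − (1 − p)^(170/196).

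| p by Day 196 | q by Day 170 | Not counted per 100 completers |
|---|---|---|
| 5% | 4.35% | 0.65 |
| 10% | 8.73% | 1.27 |
| 20% | 17.60% | 2.40 |
| 30% | 26.61% | 3.39 |

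**4. Early discontinuers.** No arithmetic applies; the two paragraphs of 8.2.2 have to be compared.

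- *As a minimum:* the first paragraph already collects all AEs and SAEs for 28 days in these patients, and the second only stresses that drug-related SAEs must not be missed.
- *As a restriction:* the second paragraph replaces the first for non-progression discontinuers, and non-serious or unrelated events after stopping are not required.

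The text does not say how the paragraphs relate. The second also stops at the start of another intervention, as 7.1 does for follow-up, whereas Table 1 has no such stop.

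**The case against.** The best defence is that 8.2.2 contains a wrong day number and nothing more. It names the end-of-study visit as the end point, and under 4.1.4 that visit is the call 28 days after EOT. With the label corrected, completers would be covered to Day 198, and the clause on early discontinuers would simply give them an equivalent period. Section 8 refers timing to the schedule of activities and treats adherence to it as essential, and 8.2 opens by requiring all AEs during the study to be recorded. A site working from Table 1 loses nothing. This stands as a reason to call the loss a risk and not a certainty. It does not remove the conflict: as printed, the day is 170 and the 28 days belong to early discontinuers.

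A reader might infer that patients who stop for toxicity get the narrowest capture, so that incidence is biased downward. The documents do not support that as fact. The second paragraph contains no word limiting collection to drug-related SAEs; the first collects AEs and SAEs for 28 days in these same patients, against 2 days for completers; and 8.3.1 requires every SAE to be reported whatever its causality.

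A reader might also take the post-trial access text as a further window. It concerns drug outside the trial supply, and Table 1's concomitant-medication row ties its 28 days to the last dose in the treatment phase. What remains is a need for clarification.

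The numerical shift is modest beside the Table 8 interval for 10 of 100, and there is no comparator or hypothesis test. A Day 170 incidence would be a legitimate shorter-window estimate if applied to everyone and labelled so. Finally, the stop at a new therapy appears in both 8.2.2 and 7.1 and looks deliberate.

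**Conclusion.** The inconsistency for completers is established from the text and affects the primary endpoint. Followed literally, 8.2.2 leaves out 26 of 28 post-dose days. The illustrative loss is about 1 to 3 patients per 100 completers for events with 10% to 30% incidence. It depends on the constant hazard and the assumed incidences, and it would be smaller if the hazard falls once the drug is stopped. How many sites would follow 8.2.2 rather than Table 1 is unknown, so this is potential undercounting and inconsistent capture, not demonstrated bias.

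For early discontinuers the finding is ambiguity of scope only. Whether collection should continue after a new anticancer therapy starts is a design choice that the documents leave unreconciled. The point should be corrected; it does not affect the sample size or Table 8.

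**What to change.** 1. Amend 8.2.2 so that all AEs and SAEs, regardless of causality, are collected in completers and early discontinuers alike from consent to 28 days after the last treatment-phase dose, as in Table 1.
2. Relabel Day 170 in 8.2.2 as the EOT visit.
3. State that the second paragraph of 8.2.2 does not narrow the first.
4. Reconcile that paragraph and 7.1 with Table 1 on whether collection ends when a new anticancer therapy starts. Flag in the analysis any events collected after that point.
5. Clarify that, for patients moving to post-trial access, the 28 days run from the last treatment-phase dose, so that the End-of-Study call still collects their AEs.
6. State the same window in SAP 6.3.1.

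The cost is a protocol amendment with ethics committee approval (Appendix A 1) and a short SAP addition. No new visit is needed, because the End-of-Study call is already scheduled.
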